#### 6.4.3 Exploratory Analysis

- The number and proportion of subjects with each individual COVID-19 symptom will be summarized on a daily basis, i.e. at 1, 2, 3, ..., 14 days, overall and by treatment group.
- In each treatment group, the incidence of the composite of COVID-19-related hospitalization, mechanic ventilation or death in the 14 days following randomization will be calculated as the number of subjects who either died, were hospitalized or required mechanic ventilation in the 14 days following randomization, divided by the number of subjects randomized to that treatment group. Number and proportion of subjects with this composite endpoint will be presented, overall and by treatment group. The incidence will be compared between treatment groups using a chi-square test. If the number of events is low, Fisher's exact test could be used.

Since this endpoint is defined in the 14 days following randomization, the delay between an event and randomization will be calculated as date of the event (date of death, date of hospitalization or date of mechanic ventilation) – date of randomization (in days), and any event for which the delay is > 14 days will be excluded from the analysis. In case the date of the event is incomplete (the exact day could be unknown, but the month and year should be known as

they are required fields), the missing event will be assumed to occur the first day of the month, unless the randomization date is after, in which case the event will be assumed to occur the day of the randomization.

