## 2 STUDY DESCRIPTION

### 2.1 Study Design

This will be a randomized, double-blind, placebo-controlled study. The study will include subjects from Quebec diagnosed with COVID-19 infections. Following informed consent, 216 subjects meeting all inclusion and no exclusion criteria will be randomized to receive either hesperidin (1000 mg q.d.) or placebo (1:1 allocation ratio) for 14 days. Investigational drug will be delivered to the patients' homes. In addition, patients will be provided with an oral electronic thermometer as well as a daily symptoms diary (see Appendix A). Follow-up phone assessments will occur after 3, 7, 10, and 14 days following randomization for evaluation of the occurrence of any trial endpoints or other adverse events. Electronic CRF (eCRF) will be completed by the research personnel over the phone with the patients.

The schedule of visits for this study is outlined in Appendix B. However, a patient may be evaluated at any time for safety concerns.

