#### 4.3 Tertiary (or Exploratory) Efficacy Endpoints

- For each of the 13 COVID-19 symptoms listed in the appendix, proportion of subjects with the symptom on a daily basis based on patient's diary. Presence of these symptoms (Yes/No) will be identified using the Covid-19 Symptoms Form of the eCRF (variables COUGH, FEVER [considered a symptom if greater than 38°], FEVERISH, STHROAT, ..., ANOS) at DAY 1 to DAY 14.
- Composite of COVID-19-related hospitalization, mechanic ventilation or death in the 14 days following randomization. These events will be identified using the Adverse Events Form of the CRF:
  - ✓ COVID-19 related hospitalization: AECOVID=YES and AESER=YES and AESHOSP=YES; date of hospitalization = ADMDAT
  - ✓ COVID-19 related mechanic ventilation: AECOVID=YES and AEVENT=YES; date of mechanic ventilation = AEVSDTA
  - ✓ COVID-19 death: AECOVID=YES and AEOUT=Fatal; date of death = AEENDAT1

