## 6 STATISTICAL METHODOLOGY

### 6.1 Determination of Sample Size

Sample size is based on the proportion of subjects with any of the following COVID-19 symptoms: fever, cough, shortness of breath or anosmia at day 7 since this time point will be the primary focus. Using a two-sided 0.05 significance level, sample sizes of 91 in both groups (182 total) will achieve 80% power to detect an absolute between groups difference of 20% in the proportion of subjects with the above COVID-19 symptoms at day 7. This is assuming that the proportions of patients with the above COVID-19 symptoms at day 7 will be 50% in the placebo group and 30% in the active treatment group. Factoring in a 15% drop out rate, a total of 216 patients will be randomized in the study (108 per group).

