### 6.2 Statistical Considerations

Baseline, efficacy and safety data will be reported using descriptive statistics. N, mean, standard deviation, median, Q1, Q3, minimum and maximum will be provided for continuous variables. Count and frequency will be provided for categorical variables.

Basic assumptions of the proposed analyses will be verified prior to the analyses. Subject disposition, datasets analyzed, baseline characteristics and efficacy analyses will be carried out on the ITT population defined in Section 3.1 according to the intent to treat principle. Safety analyses will be done on the safety population defined in Section 3.2.

All statistical tests will be two-sided and conducted at the 0.05 significance level. Statistical analyses will be done using SAS version 9.4 or higher.

A fully independent 3-member Data and Safety Monitoring Board (DSMB) will be established and will review unblinded data as detailed in the DSMB charter after randomization of 50, 100 and possibly 150 subjects. The DSMB charter will pre-specify the rules for early study termination, approved by all board members.

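### SAP 6.4.3 scores subjects lost before Day 14 without a recorded event as event-free in the hospitalization, ventilation or death composite; add a censored 14-day estimate, counts of unknown status, and one denominator

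*SAP*

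**What the plan says.** The composite is the second exploratory endpoint. SAP 6.4.3 takes the subjects with an event within 14 days of randomization, "divided by the number of subjects randomized to that treatment group", and compares arms by chi-square, with Fisher's exact test available when events are few. Events more than 14 days after randomization are left out.

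Events come from the Adverse Events Form, each with its own date (SAP 4.3, for example "date of hospitalization = ADMDAT"). The discontinuation date is held for the disposition listing (SAP 6.3.1), and Protocol 5.3 has the last call or videovisit dated in the eCRF for withdrawn patients.

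The missing-data rule in SAP 6.2.1 covers only the 13 diary symptoms. Nothing says how the composite treats a subject who leaves before Day 14 with no event on record. For symptom duration, SAP 4.2 does deal with early exit: non-completers are censored at discontinuation.

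SAP 6.4 and the title of Table 2.3.1 place the analysis in the ITT population. SAP 3.1 limits that population to randomized subjects to whom medication was delivered, without a positive pregnancy test. SAP 6.4.3 refers to subjects randomized.

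**The concern.** Keeping a subject in the denominator with no event is right if follow-up reached Day 14. If follow-up stopped at Day 3, it sets the risk from Day 3 to Day 14 to zero, which no data support.

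Outcomes are gathered mainly by telephone with the patient (Protocol 3 and 3.4), and the documents describe no hospital-record linkage or proxy contact. An admission after the last contact can therefore go unrecorded. The final call also has a window of 3 days either side (Protocol Table 1, SAP Appendix B), so even a completer called on Day 11 has three unobserved days scored as event-free.

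Two things are at stake. The absolute incidence may be too low, and the arm with more loss may look better for that reason alone. This is the only efficacy endpoint that captures severe outcomes.

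**Working it through.** **Inputs from the documents.** Two-sided 0.05 (SAP 6.2); 108 per arm and the 15% dropout allowance (SAP 6.1); 14-day window (SAP 6.4.3). **Assumed, because not given:** the true 14-day risk p, the fraction lost d, and the timing of loss.

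**The plan's own figure.** SAP 6.1 states "sample sizes of 91 in both groups (182 total) will achieve 80% power" for rates that "will be 50% in the placebo group and 30% in the active treatment group". With unpooled variance, n = (1.960 + 0.842)² × (0.25 + 0.21) / 0.20² = 90.26, so 91 per arm. Then 91 / 0.85 = 107.06, so 108 per arm and 216 in total. The figure reproduces. It concerns the Day 7 symptom endpoint; no size or power is stated for the composite.

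**Understatement when loss is unrelated to events** (constant hazard over 14 days):

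- All loss at Day 0: reported = p(1 − d).
- Loss spread evenly over Days 0 to 14: reported = p(1 − d) + d[1 − p / (−ln(1 − p))], which is close to p(1 − d/2).

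With d = 0.15:

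| Assumed true risk | Reported, even loss | Reported, Day 0 loss |
|---|---|---|
| 3% | 2.8% | 2.55% |
| 5% | 4.6% | 4.25% |
| 10% | 9.3% | 8.5% |
| 15% | 13.9% | 12.75% |

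The ratio to the true risk is about 0.93 with even loss and 0.85 with Day 0 loss. At p = 6% the reported figures are 0.06 × 0.925 = 5.55% and 0.06 × 0.85 = 5.1%. The events missed per arm are 108 × 0.0045 = 0.49 and 108 × 0.009 = 0.97.

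**Differential loss, equal true risk of 10%, 108 per arm** (rejection rates by normal approximation):

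| Loss by arm | Apparent risk ratio (even to Day 0) | Risk difference, points | Rejection rate with no true effect |
|---|---|---|---|
| 15% v 15% | 1.00 | 0 | 5.0% |
| 10% v 20% | 0.95 to 0.89 | −0.5 to −1.0 | 5.2% to 5.8% |
| 5% v 25% | 0.90 to 0.79 | −1.0 to −2.0 | 5.7% to 8.2% |

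**Does censoring recover the risk?** In a simulation with 108 per arm, 15% even loss and 4,000 runs, the SAP formula averaged 9.3% and Kaplan-Meier 10.0% at a true 10%. At a true 5% they averaged 4.6% and 5.0%.

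**When loss is related to events.** Take 15% lost at Day 0, a 10% risk in those who stay, and k times that risk in those lost. The true risk is 0.10 × 0.85 + k × 0.10 × 0.15. The SAP formula gives 8.5% for every k, and the censored estimate gives 10%.

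- k = 0: true 8.5%. The SAP formula is right and censoring overstates.
- k = 1: true 10%. Censoring is right.
- k = 2: true 11.5%. Both are too low; censoring is nearer.
- k = 3: true 13.0%. Both are too low; censoring is nearer.

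**The case against.** A good deal can be said for leaving the analysis alone, and parts of it stand.

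- **Not everyone lost is affected.** A reader might infer that anyone who leaves early is scored event-free. The documents do not support this: a subject hospitalized on Day 4 and then lost still counts as an event. Only loss without a recorded event matters, and the understatement is zero if none of those subjects had an event.
- **The 15% is not a forecast of unknown status.** "Factoring in a 15% drop out rate" is an allowance in the sample size for the Day 7 symptom endpoint. Protocol 5.3 encourages patients who stop study medication to remain for the calls to Day 14 and asks withdrawn patients to complete the Day 14 call. The fraction truly unobserved may be well below 15%.
- **Late reporting can recover events.** A subject missed at one call can report an admission at a later one, with its true date. SAP 5.2 and Protocol Appendix B collect SAEs to 21 days, though Protocol 5.2.1.1 says 14; those passages need reconciling. This helps only subjects who are reached again.
- **The size is small against the noise.** At p = 6% with 10% v 20% loss, the spurious difference is 5.7% − 5.4% = 0.3 points (even) to 5.4% − 4.8% = 0.6 points (Day 0). Its standard error is √(2 × 0.06 × 0.94 / 108) = 3.2 points.
- **A log-rank test is not clearly better.** With about 0.06 × 108 = 6 events per arm, Fisher's exact test is a sound choice, and the chi-square test agrees with Protocol 8.3.1.
- **Differential loss will be partly visible.** SAP 6.3.1 tabulates completion and reasons for discontinuation by arm.

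These points reduce the size. They do not justify assuming zero risk after loss when the dates needed to avoid that assumption are already held.

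**Conclusion.** The point holds as a modest one. The formula gives no risk to unobserved time in subjects lost without a recorded event. For an assumed true risk of 3% to 15%, 15% lost and loss unrelated to events, the reported incidence is about 0.93 to 0.85 of the true value, or about 0.5 to 1 event per arm at an assumed 6%. Less loss gives a smaller shortfall.

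Two stronger readings are not supported. One is that the treatment comparison is biased as planned. With equal loss and equal risk it is not; bias needs loss that differs between arms, and the documents give no reason to expect that. The other is that censoring would cure the problem. It recovers the risk only when loss is unrelated to the event. If patients become unreachable because they are in hospital, the censored estimate is also too low, and only counts and bounds show how much that could matter.

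The denominator mismatch between SAP 6.4.3 and SAP 3.1, 6.4 and Table 2.3.1 stands whatever is assumed about loss. The endpoint is exploratory, so no primary conclusion depends on this.

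**What to change.** In SAP 6.4.3:

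1. Report the Kaplan-Meier 14-day incidence per arm, and the difference between arms, with 95% CI. Censor event-free subjects at last contact or Day 14, whichever is first. The existing rule for incomplete event dates can stay.
2. Report per arm the number of subjects whose status at Day 14 is unknown.
3. Add a sensitivity count that scores unknown status as an event, because censoring does not remove loss related to the event. It is a bound, not an estimate: if all of the 15% allowance were unknown, it would add about 0.15 × 108 = 16 subjects per arm.
4. Keep the crude proportion with chi-square or Fisher's exact test as a supporting line.
5. Use one denominator. Reconcile the randomized count in 6.4.3 with the ITT population required by SAP 6.4 and Table 2.3.1 and defined in SAP 3.1, and state it in the table.

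The cost is SAP wording, a little more analysis work and slightly wider intervals. No new data, visits or subjects are needed.

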## 6.5 Safety Analysis

The safety analyses described in this section will be conducted on the safety population (patients who took at least one dose of study medication). Safety of hesperidin will be evaluated by presenting descriptive statistics on adverse events and serious adverse events broken down by group. No formal statistical testing is planned for the safety parameters.

### 6.5.1 Treatment Exposure

Duration of exposure will be defined as number of days on treatment (computed as date of last dose – date of first study drug dispensed + 1) for each subject of the safety population. Duration of exposure will be summarized overall and by treatment group. Duration of exposure will also be categorized according to 3 days intervals ([1-3], [4-6], [7-9], etc.) and summarized accordingly using frequencies and percentages, overall and by treatment group.

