## **5 STUDY METHODOLOGY**

### **5.1 Efficacy Outcomes**

- The **primary endpoint**:  
Proportion of subjects with any of the following COVID-19 symptoms: fever, cough, shortness of breath or anosmia, at day 3, 7, 10 and 14.
- The **secondary endpoints**:
  - 1- Mean number of COVID-19 symptoms (range 0 – 13) at day 3, 7, 10 and 14.
  - 2- Duration of COVID-19 symptoms, defined as the number of days between first symptoms and complete disappearance of any symptom.
  - 3- For each COVID-19 symptom listed in the appendix, proportion of subjects with the symptom at day 3, 7, 10 and 14.

Duration of symptoms will be determined as follows:

- If randomization and study product reception by participant occur the same day, first day of symptoms will be defined as the day of randomization;
- If randomization and study product reception by participant occur on different days, first day of symptoms will be defined as the day of study product reception.

- The **exploratory endpoints**:
  - 1- For each COVID-19 symptom listed in the appendix, proportion of subjects with the symptom on a daily basis based on patients' diary.
  - 2- Composite of COVID-19-related hospitalization, mechanic ventilation or death in the 14 days following randomization.

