#### **6.1 Medication Dispensing**

Study medication may be dispensed by the designated pharmacist according to a detailed set of dispensing instructions. Study medication will be shipped directly to the patient's home.

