#### **6.2 Dosage Regimen**

At randomization, patients will be dispensed hesperidin capsule or matching placebo. Patients will be instructed to take two capsules once daily at bedtime according to the detailed set of dispensing instructions outlined on the label.

Orally, hesperidin is generally well tolerated. Headache, asthenia, muscle cramps, and gastrointestinal side effects such as abdominal pain, dyspepsia, nausea, and diarrhea may occur in some patients. There may be unknown risks with taking the investigational product.

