## 6.3 Study Subjects

### 6.3.1 Subject Disposition

Number of subjects randomized, number of subjects who took at least one dose of study medication, number of randomized subjects completing the study and reasons for discontinuation will be summarized overall and by treatment group. A listing of subject disposition will be provided and will include subject ID, date of informed consent, date of randomization, randomized treatment group, result of the pregnancy test, day of first dose, day of last dose, completion (Yes/No), date of discontinuation and reason for discontinuation. Subject disposition will also be presented with a flow chart.

The number of days between the positive diagnosis for COVID-19 infection and the date of randomization will be summarized overall and by treatment group for the ITT population. The same will be done for the number of days between the first COVID-19 symptoms prior to randomization and the date of randomization. The first COVID-19 symptoms prior to randomization will also be displayed.

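### SAP 6.5.1 counts exposure from dispensing, so patients whose first dose comes later are credited with untreated days in the exposure table

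*SAP*

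**What the plan says.** SAP 6.5.1 states: "Duration of exposure will be defined as number of days on treatment". The same sentence gives the formula as the last-dose date minus the "date of first study drug dispensed + 1". The result is summarized by arm and also "categorized according to 3 days intervals ([1-3], [4-6], [7-9], etc".

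The protocol separates dispensing from taking the drug. Section 6.2 says "At randomization, patients will be dispensed hesperidin capsule or matching placebo", and the Timetable of Visits and Procedures (repeated in SAP Appendix B) puts dispensing at day 0. Section 6.1 says "Study medication will be shipped directly to the patient's home". Section 5.1, in its rule for duration of symptoms, covers two cases. One begins "If randomization and study product reception by participant occur the same day"; the other is reception on a different day.

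The date that the exposure formula needs is already planned. The disposition listing in SAP 6.3.1 includes "day of first dose, day of last dose". SAP 5.1 uses the date of first dose to decide whether an adverse event is treatment-emergent, with the delivery date as substitute if the first-dose date is unknown.

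**The concern.** The formula does not measure the quantity that its own sentence names. Time in transit, and any wait between delivery and the first capsule, is counted as treatment. The error can go only one way, towards longer exposure.

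It also puts two safety outputs for the same population on different clocks: treatment-emergent events start at first dose, exposure starts at dispensing. At stake is whether the exposure table can be read at face value, above all for patients who stopped early, whose true exposure is short and whose tolerability is of most interest.

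**Working it through.** The plan states no exposure figure, so there is nothing to reproduce. The check is date arithmetic.

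**Inputs**
- Start date in the formula: dispensing (SAP 6.5.1), which the protocol places at randomization, day 0 (Protocol 6.2 and timetable).
- Planned course: 14 days, once daily (Protocol 3.4), taken at bedtime (Protocol 6.2).
- Lag from dispensing to first dose, L: not given. It can be 0, because Protocol 5.1 provides for same-day receipt and a bedtime dose can follow that day. It can be 1 or more, because Protocol 5.1 also provides for receipt on a different day. I assume L = 0 to 3 days.
- Categories: 3 days wide (SAP 6.5.1). Continuing the pattern gives 13-15 and 16-18.

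**Formulas**
- Exposure as written = last dose − dispensing + 1
- Exposure from first dose = last dose − first dose + 1
- Difference = first dose − dispensing = L

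So the value as written is the first-to-last-dose span plus L, and the relative excess is L divided by that span.

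**Results** (reported days, category, excess)

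| First-to-last-dose span | L = 0 | L = 1 | L = 2 | L = 3 |
|---|---|---|---|---|
| 14 days (13-15) | 14 (13-15), 0% | 15 (13-15), 1/14 = 7% | 16 (16-18), 2/14 = 14% | 17 (16-18), 3/14 = 21% |
| 7 days (7-9) | 7 (7-9), 0% | 8 (7-9), 14% | 9 (7-9), 29% | 10 (10-12), 43% |
| 3 days (1-3) | 3 (1-3), 0% | 4 (4-6), 1/3 = 33% | 5 (4-6), 67% | 6 (4-6), 100% |
| 1 day (1-3) | 1 (1-3), 0% | 2 (1-3), 100% | 3 (1-3), 200% | 4 (4-6), 300% |

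A full course changes category only at L = 2 or more. A patient who stopped after 3 days changes category at L = 1.

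**Where the number is used.** Exposure feeds Table 3.1.1 only. The adverse event tables in SAP 6.5.2 report event totals and counts and proportions of subjects, with no person-time denominator. SAP 6.5 plans no formal safety test. No efficacy analysis in SAP 6.4 uses exposure.

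**The case against.** The strongest reply is that this is a loose phrase with little effect. Several parts of that reply stand.

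- A reader might infer that every patient is credited with untreated days, since all drug is shipped. The documents do not support that. Protocol 5.1 expressly allows receipt on the day of randomization and dosing is at bedtime, so some patients can have no excess at all.
- A reader might infer that all the safety results rest on this number. They do not: adverse event proportions use subject counts, and exposure appears in one descriptive table.
- A reader might suspect a difference between arms. Nothing in this double-blind plan suggests that the lag depends on treatment.
- A reported 15 or 16 days does not by itself prove an error. Bottles hold 32 capsules taken two a day (Protocol 6 and 6.2), which is 32/2 = 16 days of supply, so dosing beyond day 14 is physically possible. This also means that a reader of the table could not tell a lag from extra dosing.
- The SAP does not define dispensing. Its wording may be meant to separate the first bottle from a supplemental one (SAP 3.2 mentions these). If the programmed date were delivery, the transit time would drop out. But SAP 5.1 names the delivery date as a separate item, and delivery is still not first dose.
- The planned listings carry first-dose and last-dose days, so a reader with access to them could recompute exposure.

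None of this makes the formula agree with its stated definition. It limits how many patients are affected and how much that matters.

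**Conclusion.** The point holds, and it is minor. As written, SAP 6.5.1 overstates exposure by exactly the number of days from dispensing to first dose, for those patients in whom that number is above zero. On an assumed lag of 0 to 3 days, a full 14-day course is overstated by 0% to 21%; short courses are overstated by more in relative terms. How many patients are affected, and by how much, cannot be found from the documents, because they give no delivery times.

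The consequence is limited to Table 3.1.1 and its mismatch with the first-dose clock for treatment-emergent events. No test, event proportion or efficacy conclusion changes.

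**What to change.** In SAP 6.5.1, compute duration of exposure as date of last dose minus date of first dose plus 1. Where the first-dose date is unknown, use the study medication delivery date, matching SAP 5.1, and report how many patients needed that substitute, since it can still overstate exposure.

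Label the result a first-to-last-dose span. Missed doses are not replaced (Protocol 3.4) and drug may be withheld for a time (Protocol 5.3), so a date span counts those days whichever start date is used.

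The cost is one line of SAP text and the matching line of programming. Both dose dates are already planned for the disposition listing, so no new data are needed.
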